5.6. Estimated sample size

The number of samples in this study was calculated twice because the dependent variables observed were the amount of bleeding and the need for postoperative blood transfusion, all of which were numerical variables. From the overall calculation results, the largest sample size for this study was taken, then 10% was added to accommodate the possibility of *dropping out*. The formula used in the sample calculation for both variables is the hypothesis test formula for the mean of two independent groups. The literature used as a reference for calculating the sample of this study is a study by Chaudhary et al. (2018).⁴⁴ The following are the sample calculation results for each research variable.

- **A variable amount of bleeding**

$$n_1 = n_2 = 2 \left[\frac{(z_\alpha + z_\beta)s}{(x_1 - x_2)} \right]^2$$
$$n_1 = n_2 = 2 \left[\frac{(1,96 + 0,842)339,021}{300} \right]^2$$
$$n_1 = n_2 = 20,05 \sim 20 \text{ sample}$$

Description:

= normal standard deviation for type I error with α is 0.05 (1.96)

= normal standard deviation for type II error with β is 0.2 (0.842)

= standard deviation between placebo and treatment groups according to the study (placebo = 445.941 mL and treatment = 232.101 mL, so that the mean value taken = 339.021 mL)⁴⁴

= expected clinical difference (taken 300 mL)

- **Variable blood transfusion needs**

$$n_1 = n_2 = 2 \left[\frac{(z_\alpha + z_\beta)s}{(x_1 - x_2)} \right]^2$$

$$n_1 = n_2 = 2 \left[\frac{(1,96 + 0,842)1,072}{1} \right]^2$$

$$n_1 = n_2 = 18,04 \sim 18 \text{ sample}$$

Description:

= average standard deviation for type I error with α is 0.05 (1.96)

= average standard deviation for type II error with β is 0.2 (0.842)

= standard deviation between placebo and treatment groups according to the study (placebo = 1.225 units and treatment = 0.918 units so that the mean value taken = 1.072 units)⁴⁴

= expected clinical difference (taken as 1 unit)

Based on the above calculation results, 20 patients were taken as the minimum sample size for each placebo and treatment group. With the addition of 10% to anticipate dropouts (2 patients per group), the total sample for each group was 22 samples. The total sample for both groups was 44 patients. In this study, there are three arms group (CABG group, OPCAB group, and Valve Surgery group). The total sample for both arms group was 132 patients.

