3.12. Data processing flow

The data of the research subjects collected using the forms were verified and compiled using SPSS software for Microsoft Windows version 20.0 in the form of descriptive tables. Data normality and statistical analysis for each variable were performed using the same software. The tests used to analyze the two dependent variables (amount of bleeding and blood products transfusion after cardiac surgery) were the independent T-test (for normal data distribution) and the Mann-Whitney test (for abnormal data distribution).

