1.4 Detailed cost plan

| | |
|--|------------------------|
| Proposal drafting (printing and photocopying costs) | Rp600.000,00 |
| Submission of ethics and research permits | Rp900.000,00 |
| Data collection (observation, consumables) | Rp15.000.000,00 |
| Preparation of research report (printing and photocopying costs) | Rp1.500.000,00 |
| Journal publication | Rp5.000.000,00 |
| Total | Rp23.000.000,00 |

1.5 *Dummy table*

Tabel Error! No text of specified style in document..1 Sample table of experimental and control group characteristics

| Variables | Experimental Group | Control Group (Placebo) | P-value |
|---------------------------------------|--------------------|-------------------------|---------|
| Age (years) | Rerata ± SD | Rerata ± SD | |
| Gender | | | |
| Male | n (%) | n (%) | |
| Women | n (%) | n (%) | |
| Body surface area (m ²) | Mean ± SD | Mean ± SD | |
| Comorbidities | | | |
| Hypertension | n (%) | n (%) | |
| Diabetes mellitus | n (%) | n (%) | |
| Preoperative hemoglobin | Mean ± SD | Mean ± SD | |
| Preoperative hematocrit | Mean ± SD | Mean ± SD | |
| Preoperative APTT | Mean ± SD | Mean ± SD | |
| Preoperative INR | Mean ± SD | Mean ± SD | |
| Preoperative creatinine | Mean ± SD | Mean ± SD | |
| Postoperative hemoglobin | Mean ± SD | Mean ± SD | |
| Duration of aortic cross clamp | Mean ± SD | Mean ± SD | |
| Duration of use of heart-lung machine | Mean ± SD | Mean ± SD | |

Tabel Error! No text of specified style in document..2 Sample output table of CABG results in experimental and control groups

| Primary outcome output | Control group (n=22) | Experimental group with TXA (n = 22) | P-value |
|----------------------------------|----------------------|--------------------------------------|---------|
| Volume of chest drain bleeding | | | |
| Initial bleeding (mL) | Mean ± SD | Mean ± SD | |
| 6-hour bleeding (mL) | Mean ± SD | Mean ± SD | |
| 24-hour bleeding (mL) | Mean ± SD | Mean ± SD | |
| 48-hour bleeding (mL) | Mean ± SD | Mean ± SD | |
| Blood Transfusion | | | |
| PRC transfusion (mL) | Mean ± SD | Mean ± SD | |
| FFP transfusion (mL) | Mean ± SD | Mean ± SD | |
| TC transfusion (mL) | Mean ± SD | Mean ± SD | |
| Cryoprecipitate transfusion (mL) | Mean ± SD | Mean ± SD | |

Table Error! No text of specified style in document..3 Sample output table of OPCAB results in experimental and control groups

| Primary outcome output | Control group (n=22) | Experimental group with TXA (n = 22) | P-value |

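### The bleeding sample size averages the two SDs rather than the variances, so 20 per group gives about 76% power for 300 mL, not 80%

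*Combined protocol and SAP*

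**What the plan says.** Section 5.6 (Estimated sample size) uses n = 2[(z_α + z_β)s/(x₁ − x₂)]² for two independent means with equal groups. Its inputs for bleeding are:

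- "normal standard deviation for type I error with α is 0.05 (1.96"), which is a two-sided 5% test;
- "normal standard deviation for type II error with β is 0.2 (0.842"), which is 80% power;
- a difference of 300 mL;
- a single SD formed from two values in one published study: "placebo = 445.941 mL and treatment = 232.101 mL, so that the mean value taken = 339.021 mL".

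The result is 20.05, taken as 20. Transfusion gives 18.04, taken as 18. Bleeding therefore sets the size: "20 patients were taken as the minimum sample size for each placebo and treatment group". The section continues: "With the addition of 10% to anticipate dropouts (2 patients per group), the total sample for each group was 22 samples". The same 22 + 22 is then applied in each surgery type: "In this study, there are three arms group (CABG group, OPCAB group, and Valve Surgery group"). That makes 44 × 3 = 132 patients.

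Section 3.12 names the "independent T-test (for normal data distribution") as the test, with Mann-Whitney if the data are not normal. The outcome tables in section 1.5 are laid out for 22 per group ("Control group (n=22")).

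**The concern.** The variance of a difference between two means, with n in each group, is (s₁² + s₂²)/n. The formula writes this as 2s²/n, so s² has to be the average of the two variances. The section averages the SDs instead. The mean of two unequal SDs is always smaller than their root mean square, so this error can only make the required sample look smaller. Here the SDs differ by a factor of 445.941/232.101 = 1.92, enough for the gap to matter.

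Bleeding is the variable that fixed the sample size, and the same number serves three separate comparisons, each with its own bleeding hypothesis in section 1.4. If the stated β is wrong, it is wrong in all three. A non-significant result in any one of them would be read against more power than the design has at its stated minimum.

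**Working it through.** **Inputs (all from section 5.6).** s₁ = 445.941 mL (placebo), s₂ = 232.101 mL (treatment), difference 300 mL, z_α = 1.96, z_β = 0.842, 20 per group before dropouts and 22 enrolled.

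**1. Reproduce the plan.**
- Mean SD = (445.941 + 232.101)/2 = 339.021 mL.
- n = 2 × [(1.96 + 0.842) × 339.021/300]² = 20.05.
- Power at 20 = Φ(300/(339.021 × √(2/20)) − 1.96) = Φ(0.838) = 79.9%.

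The plan's figure is reproduced. Rounding 20.05 down to 20 costs only about 0.1 percentage point.

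**2. Correct the SD.**
- s = √((445.941² + 232.101²)/2) = √126,367 = 355.48 mL.
- The plan's variance is 339.021² = 114,935 mL². The shortfall is ((445.941 − 232.101)/2)² = 11,432 mL², and 11,432/126,367 = 9%.

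**3. Recompute n.** n = 2 × [2.802 × 355.48/300]² = 22.05. Like for like, this is 22 against 20 by the plan's rounding down, or 23 against 21 by rounding up.

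**4. Recompute power for 300 mL.** On the normal approximation at 20 per group: Φ(300/(355.48 × √(2/20)) − 1.96) = Φ(0.709) = 76.1%. The t-test column uses the noncentral t distribution.

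| Evaluable per group | SD (mL) | Normal approximation | t-test |
|---|---|---|---|
| 20 | 339.021 (plan) | 79.9% | 77.8% |
| 20 | 355.48 | 76.1% | 73.9% |
| 21 | 355.48 | 78.1% | 76.1% |
| 22 | 355.48 | 79.9% | 78.1% |

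The SD error costs about 4 points on either scale. Using the normal approximation in place of the t-test is a separate matter worth about 2 more. A simulation of the pooled t-test on normal data with the two unequal SDs (200,000 runs) agrees: 74.0% at 20 and 78.1% at 22.

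**5. Difference detectable at 80% power.** At 20 per group: 2.802 × 355.48 × √(2/20) = 315 mL (323 mL by t-test). At 22: 300 mL (307 mL by t-test).

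**6. Transfusion.** s = √((1.225² + 0.918²)/2) = 1.082 units. This gives n = 18.40, and power for 1 unit at 20 per group is 83.2% (81.2% by t-test). The same averaging does no harm there.

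Power for the Mann-Whitney alternative cannot be computed, because the documents give no distribution shape.

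**The case against.** The strongest reply is that the trial enrols 22 per group, not 20. With all 22 evaluable, the corrected power on the plan's formula is 79.9%, the same value the plan's SD gave at 20. On that reading the design falls short only as far as dropouts occur. The arithmetic is right. But the section itself names 20 as the minimum and gives the other 2 as a dropout allowance, and section 5.5.2 defines the intraoperative events that remove a patient. The corrected SD uses up that whole allowance, so the protection against dropout that the section claims is absent for bleeding.

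Three further points are fair and limit the claim:

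- The plan's sums are correct as sums, and it says openly that a mean was taken. The fault lies in what was averaged.
- The two SDs come from one outside study and are applied unchanged to CABG, OPCAB and valve surgery. True power in each could lie on either side of 76%. What is shown is that the stated β does not follow from the quoted SDs.
- A change of 4.9% in the SD and about 4 points of power is small. It alters no estimate, test or trial procedure.

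None of these makes 80% the right figure at 20 per group.

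**Conclusion.** The concern holds. On the plan's own inputs and normal approximation, 20 evaluable patients per group give 76.1% power for a 300 mL difference in bleeding. That is a β of about 0.24 where the section states 0.20. By the planned t-test, power is 73.9%. With 22 evaluable it is 79.9% (78.1% by t-test).

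These figures assume that the quoted SDs apply in each surgery type, that groups are equal, that the test is two-sided at 5% and, for the t-test figures, that the data are normal. The finding concerns bleeding only; the transfusion target survives correction. The effect is modest, but the error sits in the calculation that sets the size of all three comparisons.

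**What to change.** In section 5.6, replace 339.021 mL with s = √((445.941² + 232.101²)/2) = 355.5 mL. Keep 22 per group and 132 in total. Then make one of two statements for each surgery type:

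- Power for 300 mL is about 76% (74% by t-test) with 20 evaluable per group, and about 80% (78% by t-test) with 22.
- With 20 evaluable per group, the difference detectable at 80% power is about 315 mL (323 mL by t-test).

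For consistency, use 1.082 units in the transfusion calculation; its conclusion does not change.

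The cost is rewording one section and accepting a slightly lower stated power. No patients are added and the analysis is unchanged. This is free only because the claim is lowered. Holding 80% power would need 23 evaluable per group (24 by t-test). Adding the plan's 10% to a corrected minimum of 22 or 23 gives 22 × 1.1 = 24.2 or 23 × 1.1 = 25.3. That is 25 to 26 enrolled per group, or 150 to 156 in total over the six groups.

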3.7.3. Post-surgery

Patients were intensively treated in the intensive care unit (ICU), intermediate room, and standard room according to clinical conditions. The researcher observed and recorded the amount of bleeding accumulated until chest tube removal and blood products transfusion units of blood components during treatment. Transfusion will be given when there is an indication for transfusion. The indication for *packed red cell* (PRC) transfusion was Hb <10 g/dL, with a target of Hb >10 g/dL. The indication for platelet transfusion was platelets <100,000 U/ μ L, with a target of platelets >100. The indication for fresh frozen plasma (FFP) transfusion is if APTT > 1.5 times the control, the transfusion target is activated partial thromboplastin clotting time (APTT) < 1.5 times the control. Cryoprecipitate was given if fibrinogen < 100 mg/dL, and the transfusion target was fibrinogen > 100 mg. Observation of bleeding was recorded from initial

bleeding, 6 hours, 24 hours, and 48 hours, or until chest tube removal if the bleeding was <200 mL/24 hours.

Bleeding management protocols were performed if there was excessive or massive bleeding post-surgery. A single researcher conducted all observations to maintain data reliability which was then recorded for further processing.

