3.10. Operational Definition

Table 3.2 Operational definitions-

| Variables | Definition | Measurement | Variable Scale | Variable Value |
|--|--|---|----------------|--|
| Administration of topical tranexamic acid | Intrapericardial administration of 5 g tranexamic acid in 50 mL 0.9% NaCl after protamine administration and before sternotomy closure in cardiac surgery | - | Nominal | 
 • Treatment (tranexamic acid) • Control (NaCl 0.9%) |
| Amount of bleeding | | | | |
| Initial bleeding | Amount of blood accumulated in the patient's water-sealed drainage (WSD) system shortly after cardiac surgery | Observation of the volume of blood collected in the WSD system | Numerical | mL |
| 6-hour bleeding | Amount of blood accumulated in the water-sealed drainage (WSD) system of a patient 6-hour post cardiac surgery | Observation of the volume of blood collected in the WSD system | Numerical | mL |
| 24-hour bleeding | Amount of blood accumulated in the water-sealed drainage (WSD) system of a patient 24 hour-post cardiac surgery | Observation of the volume of blood collected in the WSD system | Numerical | mL |
| 48-hour bleeding | Amount of blood accumulated in the water-sealed drainage (WSD) system of a patient 48 hours- post cardiac surgery | Observation of the volume of blood collected in the WSD system | Numerical | mL |
| Blood Transfusion Requirements | | | | |
| Packed red cell (PRC) transfusion | Amount of PRC transfusions received in post cardiac surgery patients with Hb levels <10 g/dL to reach Hb levels >10 g/dL before discharge. | Observation of the volume of PRC received by the patient | Numerical | mL |
| Platelet transfusion ⁴⁹ | Amount of blood platelet transfusions received in post cardiac surgery patients with platelets <100,000 U/ μ L to reach levels of 100,000 U/ μ L or in platelet dysfunction. | Observation of the volume of Platelet transfusion received by the patient | Numerical | mL |
| Fresh Frozen plasma (FFP)Transfusion ⁴⁹ | Amount of blood FFP transfusions received by post cardiac surgery patients with international normalized ratio (INR) >1.5 to reach 1.5 | Observation of the volume of FFP received by the patient | Numerical | mL |

| Variables | Definition | Measurement | Variable Scale | Variable Value |
|---|---|--|----------------|---|

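### The transfusion power calculation is for one unnamed variable in units, but four component volumes in mL are tested per surgery group and none is identified as the powered outcome

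*Combined protocol and SAP*

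**What the plan says.** - **Section 5.6 (Estimated sample size)** makes one calculation for bleeding and one for transfusion need, both with the "hypothesis test formula for the mean of two independent groups". The transfusion calculation has one variable, in units. Its SDs are "placebo = 1.225 units and treatment = 0.918 units so that the mean value taken = 1.072 units", and its effect is the "expected clinical difference (taken as 1 unit". No blood component is named and no total is mentioned. The result is 18 per group. The plan adopts 20 from the bleeding calculation, and 22 after adding two for dropout.
- **Section 3.7.3 (Post-surgery)** has the researcher record "blood products transfusion units of blood components during treatment". Section 3.8 (Instruments used) says the form holds transfusion units.
- **Section 3.10, Table 3.2** defines four transfusion outcomes (PRC, platelets, FFP, cryoprecipitate), each a volume. The PRC entry reads "Observation of the volume of PRC received by the patient | Numerical | mL".
- **Section 1.5 (Dummy table)** gives one outcome table each for CABG, OPCAB and valve surgery. Each lists "PRC transfusion (mL" and the matching mL rows for FFP, platelets and cryoprecipitate, with a P-value column, under a heading that calls them primary. There is no total row.
- **Section 1.4 (Hypothesis), items 4 to 6,** states one overall transfusion hypothesis per surgery group. Section 3.12 treats transfusion as one of two dependent variables, tested by t-test or Mann-Whitney.

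No unit-to-mL conversion is given for any component.

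**The concern.** Transfusion is one of the two dependent variables and the subject of three of the six hypotheses, so a reader will expect the 80% power to belong to a transfusion result in the report. As written, it cannot be assigned to one. The calculation describes one quantity and the results tables hold four, on another scale, without a sum.

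There are two consequences. First, a non-significant component row could be read as a well-powered null when its power is unknown. Second, each hypothesis names one quantity but receives four P-values. With no lead row and no adjustment, the choice of row that answers the hypothesis can be made after the data are seen.

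**Working it through.** **1. The plan's own figure.** Inputs from section 5.6: z = 1.96, from "average standard deviation for type I error with α is 0.05 (1.96"); z = 0.842, from "average standard deviation for type II error with β is 0.2 (0.842"); SD = (1.225 + 0.918)/2 = 1.0715, taken as 1.072; difference 1 unit.

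n per group = 2 × [(1.96 + 0.842) × 1.072 / 1]² = 2 × (3.0037)² = 18.04

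This reproduces (18 in the plan; 19 if rounded up). Bleeding gives 2 × [(1.96 + 0.842) × 339.021 / 300]² = 20.05, so bleeding sets n.

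**2. Power for 1 unit at 20 per arm.** The standardised shift is (1/1.072) × √(20/2) = 2.950. By normal approximation, power = Φ(2.950 − 1.96) = 83.9%. By noncentral t it is 82.0%, or 81.2% with the root-mean-square SD of 1.082.

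**3. Does the change from units to mL matter by itself?** If one unit of a named component is v mL, the difference becomes v and the SD 1.072v, and the ratio is unchanged. With v assumed at 150 to 350 mL, n stays 19 (rounded up) and power stays 83.9%. This holds for one component of fixed volume. For a total, mL is a constant multiple of units only if all components have the same volume per unit.

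**4. Power for one component row.** The documents give no component SD or expected difference, so this can only be bracketed. Suppose 1 unit and SD 1.072 describe a total, and a component carries share f of the effect and share s of the SD. The shift is then 2.950 × f/s (normal approximation, 20 per arm):

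| Share of effect f | Share of SD s | Power | n per arm for 80% |
|---|---|---|---|
| 0.5 | 1 | 31% | 73 |
| 0.5 | 0.75 | 50% | 41 |
| 0.5 | 0.5 | 84% | 19 |
| 0.25 | 1 | 11% | 289 |
| 0.25 | 0.75 | 16% | 163 |
| 0.25 | 0.5 | 31% | 73 |

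Four equal independent components (SD 1.072/√4 = 0.536, difference 0.25 each) give 31% per row. Four equal, perfectly correlated components (SD 1.072/4 = 0.268) give f/s = 1 and so 84%. A component whose SD shrinks faster than its effect does better still: f = 0.75 with s = 0.5 gives 99%. If the source variable is PRC alone, PRC keeps the 82% and nothing is known about the other three rows.

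**5. Multiplicity.** Four unadjusted tests at 0.05 per surgery group, if independent: 1 − 0.95⁴ = 18.5%. Over all 12 tests: 1 − 0.95¹² = 46.0%. Positive correlation between components would lower both figures.

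**The case against.** The strongest reply is that this is a labelling inconsistency with little design consequence. Each part deserves an answer.

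- *The data are recorded in units, so the powered variable can be analysed.* Correct. A reader of Table 3.2 might infer that transfusion is collected only in mL, but sections 3.7.3 and 3.8 say units. The documents disagree with themselves, and the needed data should be on the form.
- *Units against mL cannot affect power.* Correct for one component of fixed volume (step 3). A reader might infer that the switch of scale voids the calculation; it does not.
- *The power may belong to the PRC row.* Possible. A reader might infer that the stated power applies to no analysed outcome. That is too strong: if the source SDs are PRC units, the power carries over to PRC. The documents do not say, and that silence is the point.
- *Low component power is an artefact of the scenario.* Partly right. The 11% case gives one component the full SD of the total with a quarter of the effect. If components are not negatively correlated, the other three would then have no variance while carrying the rest of the effect. Quoting only 11% or 31% would mislead; the range is the honest statement.
- *The dummy tables are only samples, and sections 1.4 and 3.12 leave room for one overall test.* They do, but no section defines that overall quantity, and Table 3.2 defines the same four volumes as the dummy tables.

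What remains is that the powered variable is unidentified and that four tests stand in for each hypothesis.

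**Conclusion.** The point holds in a limited form. Section 5.6 powers one transfusion quantity that the plan never identifies. At most one of the four component rows per surgery group can match it, and none does if it is a total. Each of hypotheses 4 to 6 is answered by four unadjusted tests, with familywise error about 18.5% per surgery group under independence.

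The 82% power at 20 per arm is sound for a 1-unit difference with SD 1.072. Component power is not computable from the documents. The 11% to 84% range rests on assumed shares: a component carrying a half or a quarter of the effect, with between its proportionate share and all of the SD.

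A reader might also infer that the trial is too small. The documents do not support that on this ground, since bleeding required 20 per group against 18 for transfusion. This should be corrected, but it does not undermine the design.

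**What to change.** - In section 5.6, Table 3.2 and the dummy tables, name one transfusion outcome per surgery group for hypotheses 4 to 6. State it in units to discharge, and match it to the variable behind the 1.225 and 0.918 SDs: total units, or PRC units if that is what the source reports.
- Check that source. Section 5.6 cites it as reference 44, but the 2018 trial of topical tranexamic acid in open heart surgery is number 48 in the list.
- Use one scale in sections 5.6, 3.7.3, 3.8, 3.10 and 1.5 (Dummy table). If mL volumes are kept, state the conversion for each component.
- Label the remaining component rows as secondary, and say that the 80% power applies only to the named outcome.

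The cost is wording, since units are already on the form, and n need not change. The price is that the other components become supportive only. Keeping all four as primary with a Bonferroni correction would cost more: at 0.05/4, power for a 1-unit difference at 20 per arm falls to about 67% (normal approximation), and 80% would need 26 per arm.
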